It is expected that as from June 2006 the indications of HUMIRA®(adalimumab) will be extended with the treatment of adults with active ankylosing spondylitis who have had an inadequate response to conventional therapy. This amendment will be of application after the indication has been approved by EMEA.

For this PMOS, the follow-up observation period is planned for 5 years and is focussed on safety information as well as maintenance of efficacy parameters for HUMIRA®(adalimumab) during normal clinical practice.

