2 STATISTICAL ANALYSIS

The analysis of the baseline data and prior anti-TNF treatment will be performed broken down by indication (RA, PsA, AS). Within each indication, baseline data will also be presented broken down by completed/not completed patients. Statistical tests will be performed to compare baseline data for patients completed/not completed the study.

The analysis of treatment duration and the evolution of different parameters over time, will be performed broken down by indication (RA, PsA, AS).

The analysis of adverse events will be performed for all patients together and broken down by indication (RA, PsA, AS):

- Overall
- Per year (up to 5 years)
- By cumulative yearly period (till 5 years)
- Incidence
- Incidence divided by total exposure to treatment (till 5 years).
- Reason for seriousness
- Serious adverse events: number of patients and incidence by system organ class and preferred term
- Non-serious adverse events: number of patients by system organ class and preferred term

If an adverse event has no onset date, the observation date will be taken as onset date. Events that are coded with multiple MedDRA Terms will be counted as separate event.

The percentages in the adverse event table are calculated as follows:

Table	Nominator	Denominator
Number of patients with an adverse event per year.	Number of patients treated in that year with at least one adverse event in that year.	Number of patients treated in that year.
Number of patients with an adverse event per cumulative year	Number of patients with at least one adverse event in that year or before.	Number of patients.
Number of adverse events by total exposure to treatment	Number of adverse events in that year or before.	The sum of the patients' treatment exposure time in that year or before.

The following tables will be presented:

Rheumatoid Arthritis

- 1 Baseline Characteristics– All Patients and Broken Down by Early Termination**
 - 1.1 Age
 - 1.2 Gender
 - 1.3 Disease Duration Before Inclusion
 - 1.4 Anti-TNF use Before Inclusion
 - 1.4.1 Anti-TNF Naïve / Experienced
 - 1.4.2 Types of Anti-TNF use Before Inclusion
 - 1.5 Physician's Assessment of Disease Activity
 - 1.6 Clinical Examination
 - 1.6.1 Joint Assessment (tender joints count, swollen joints count)
 - 1.6.2 Inflammatory Parameters (CRP, ESR)
 - 1.6.3 Physical Function (HAQ %)
 - 1.7 Concomitant Medication
 - 1.7.1 Concomitant Steroids
 - 1.7.2 Concomitant NSAIDs
 - 1.7.3 Concomitant Immunomodulators

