3.1.2 Patients with Adverse Events by MedDRA System Organ Class

3.1.3 Patients with Adverse Events by MedDRA System Organ Class and Preferred Term

3.2 Adverse Events per Year

3.2.1 Patients with Adverse Events, Patients with Serious Adverse Events, Patients with Fatal Adverse Events and Patients with Adverse Events Causing Treatment Discontinuation

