3.4.2 Number of Adverse Events by MedDRA System Organ Class

3.4.3 Number of Adverse Events by MedDRA System Organ Class and Preferred Term

3.5 Incidence Adverse Events Divided by Total Exposure to Treatment

3.5.1 Number of Adverse Events, Serious Adverse Events, Fatal Adverse Events and Number of Adverse Events Causing Treatment Discontinuation

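### The exposure-adjusted adverse event rate is cumulative only and dilutes a late change; the year-specific view is a patient percentage without person-time.

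*SAP*

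**What the plan says.** SAP section 2 lists several adverse event displays. One is "Incidence divided by total exposure to treatment (till 5 years"). The numerator and denominator table in that section defines it once: the numerator is "Number of adverse events in that year or before", and the denominator sums the patients' "treatment exposure time in that year or before". The outputs are tables 3.5.1-3.5.3, under "3.5 Incidence Adverse Events Divided by Total Exposure to Treatment".

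A separate display, "3.2 Adverse Events per Year" (tables 3.2.1-3.2.3), is specific to each year. Its numerator is "Number of patients treated in that year with at least one adverse event in that year" and its denominator is "Number of patients treated in that year". It covers any, serious, fatal and treatment-stopping events, then system organ class and preferred term, for each indication and for all patients together.

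SAP 1.5 assigns events to five disjoint yearly windows by onset. Year 5 runs from day 1461 to day 1826.25. The same section calls a patient completed from 1734 days of study duration, ends a completer's treatment duration at the last visit, and treats temporary stops as time on drug.

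The Protocol introduction says that "the follow-up observation period is planned for 5 years and is focussed on safety information".

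**The concern.** A five-year safety study invites the question whether risk changes with time on treatment. Protocol 3.2.1 asks for special attention to events such as malignancy, for which that question is natural. The one planned measure that accounts for exposure cannot answer it directly. Its year-5 column mixes year 5 with the four earlier years, which hold most of the patient-years because patients leave over time. A reader who compares the yearly columns of tables 3.5 would see a late rise much reduced in size.

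The year-specific tables 3.2 do not fill the gap completely. They count patients, not events, and use a head count in place of time at risk.

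**Working it through.** The documents state no event rate, exit rate or patient-years for these tables, so there is no planned figure to reproduce. The only available check is the patient total in SAP 1.2: 2836 + 1127 + 1957 = 5920, which agrees.

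**Assumptions (not in the documents).** Constant yearly exit d of 0, 10, 20 or 30%. A constant base event rate that doubles in year 5, or in years 4 and 5.

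**1. Dilution in tables 3.5.** With h = -ln(1 - d), patient-years in year k per starting patient are PY_k = [exp(-h(k-1)) - exp(-hk)]/h, or 1 when d = 0. If the rate doubles in year 5 only, the cumulative rate at year 5 equals the base rate × (1 + PY_5 / ΣPY). Starting from 5920 patients:

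| Yearly exit | PY_5 | ΣPY | Rise, year 5 doubles | Rise, years 4-5 double | Cumulative rate at year 5, base 5 per 100 PY, year 5 doubles |
|---|---|---|---|---|---|
| 0% | 5920 | 29600 | 20% | 40% | 6.00 |
| 10% | 3686 | 23010 | 16% | 34% | 5.80 |
| 20% | 2173 | 17837 | 12% | 27% | 5.61 |
| 30% | 1196 | 13808 | 9% | 21% | 5.43 |

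A rate of year-5 events over year-5 patient-years would show 10.0 per 100 in every row, twice the base.

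**2. What tables 3.2 would show.** With event rate l, the expected percentage with an event among those treated at the start of the year is l/(l + h) × [1 - exp(-(l + h))]. At 5 per 100 PY and 20% exit (h = 0.223) this is 4.38%. At 10 per 100 PY it is 8.55%, a ratio of 1.95. For base rates of 1 and 5 per 100 PY and exit of 0-30%, the ratio of year 5 to year 1 is 1.95 to 1.99. Most of the doubling is visible.

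**3. Where tables 3.2 fall short.**

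- *Short year 5.* A completer last seen on day 1734 contributes 1734 - 1461 = 273 of 365.25 days, or 75%, but counts as a whole patient. At a constant rate, the year-5 percentage can be understated by up to about 25%, depending on last-visit dates. If all year-5 follow-up ended on day 1734, a true doubling would appear as roughly 2 × 0.75 = 1.5.
- *Exit within the year.* At a constant 5 per 100 PY, the percentage falls from 4.76% to 3.83% as in-year exit goes from 5% to 40%, with no change in risk.
- *Common events.* At 20% exit, a doubling from 50 to 100 per 100 PY shows as 35.6% to 57.7% (1.62 times). A doubling from 100 to 200 shows as 57.7% to 80.2% (1.39 times). Repeat events in one patient within a year are not counted.

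**4. Recovery by subtraction.** With E_k and P_k the cumulative events and patient-years to the end of year k, (E_5 - E_4)/(P_5 - P_4) returns the year-5 rate exactly. This works only if both counts and patient-years are printed, and the SAP does not say that they will be.

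**The case against.** The strongest reply is that the plan already has a year-specific analysis. Earlier years do not enter tables 3.2, which are produced at every level of detail and for every population. For an uncommon event counted once per patient, as malignancy usually is, a yearly patient percentage follows a yearly rate closely. Even in the worst case for year-5 follow-up, a doubling appears there as about 1.5, well above the 1.09 to 1.20 in tables 3.5. This stands, and it limits the point.

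A reader might infer from tables 3.5 alone that a late risk would vanish from the safety analysis, or that the report would call the risk stable over five years. The documents do not support this. Tables 3.2 would show such a rise for uncommon events, and the SAP nowhere says that statements on change over time will rest on tables 3.5.

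It is also fair that a cumulative rate is valid for what it is labelled. Protocol 5.1.2 promised only frequencies and percentages for adverse events, and Protocol section 5 rules out inferential techniques. The SAP gives more than that, so the change is an improvement and not the repair of a contradiction.

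What remains is that no planned table relates a year's events to that year's time at risk. The head count departs from a rate where follow-up is partial, events recur or events are common.

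**Conclusion.** The point holds as a limited one. The exposure-adjusted rate is defined only cumulatively. A doubling in year 5 lifts its year-5 figure by 9-20%, and a doubling in years 4-5 by 21-40%, across assumed yearly exit of 30% to 0%. These figures rest on that assumed range and on constant exit. A reader might try to narrow the range from the record counts in SAP 1.2, but those describe the table before duplicates, misclassified visits and added pages were dealt with, so they are not a sound basis.

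The year-specific percentages in tables 3.2 offset much of the dilution for uncommon events (a ratio of about 1.95-1.99, or roughly 1.5 if all year-5 follow-up ends on day 1734). They do not replace a yearly rate, and their year-5 value can be low by up to about 25% for reasons unrelated to risk. The change is worth making because it is cheap.

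**What to change.** Add a row to the numerator and denominator table in SAP section 2, and matching columns to tables 3.5.1-3.5.3. For each of years 1-5 they should give:

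- the number of adverse events with onset in that year, using the SAP 1.5 windows;
- the treatment patient-years accrued in that year;
- the ratio of the two.

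Keep the cumulative columns. State in the SAP that comments on change over time rest on the year-specific rates, read alongside tables 3.2.

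The cost is SAP wording and extra columns. No new data are needed: the onset windows exist, and the cumulative denominator already requires exposure to be cut at each year end.

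There are three limits to state with the rates. Later years rest on fewer patient-years and are less precise, which the printed counts will show. Later-year rates describe patients still on drug, since Protocol section 3 takes patients out of the study when treatment is permanently discontinued. The rates also inherit the SAP 1.5 rule that temporary stops count as exposure.

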3 INVESTIGATIONAL PLAN

This is a multi-center, uncontrolled observational study of patients who at the time of entry were prescribed with HUMIRA®(adalimumab) following normal clinical practice, with or without other anti-rheumatic treatments, prior to enrollment in this study.

Patients will be followed for 5 years within the post-marketing observational study.

Physicians will be provided with a study kit that includes a protocol, patient informed consent forms, adverse event report forms, and Data Report Forms (DRFs), for each patient to be enrolled. The participating physician will already have provided a prescription to the patient for HUMIRA®(adalimumab), along with instructions for appropriate use according to the European Union (EU) Summary of Product Characteristics (SPC).

Once the physician has determined that the patient meets the inclusion criteria, and the patient has agreed to be included in the observational study, the patient's baseline demographic data, and disease status will be reported in the Baseline DRF. The physician will then follow-up the patient via regular office visits at intervals as determined by routine clinical practice or as recommended by national guidelines.

Patient's safety and efficacy data if they are part of clinical routine will be recorded in the DRFs at Baseline, and regular visits which are closest to Month 3, Month 6, Month 9, Month 12, Month 18, Month 24, Month 30, Month 36, Month 42, Month 48, Month 54, and Month 60. While the physician will likely deem it appropriate and necessary to have the patient return for intermediate visits during the study period, data will be collected via DRFs only at the intervals which correspond closely to those described above. Physicians are encouraged to treat their patients as they would in their routine clinical practice. If treatment with HUMIRA®(adalimumab) is permanently discontinued for any reason, patients will be discontinued from the study and the reason should be recorded. Physicians will be asked to record adverse events up to 3 months after last administration of HUMIRA®(adalimumab) on the DRF of the next scheduled data collection time.

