3.5.2 Number of Adverse Events by MedDRA System Organ Class

3.5.3 Number of Adverse Events by MedDRA System Organ Class and Preferred Term

3.6 Reasons for Seriousness for Serious Adverse Events

3.7 Serious Adverse Events

3.7.1 Patients with Adverse Events by MedDRA System Organ Class and Preferred Term

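### The fatal row of the exposure-based adverse event table can count one death more than once, and no table gives patients with a first event per patient-year

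*SAP*

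**What the plan says.** SAP section 2 sets out a numerator and a denominator for three kinds of adverse event table. For the exposure-based kind the numerator is "Number of adverse events in that year or before" and the denominator is "The sum of the patients' treatment exposure time in that year or before". The same section adds a counting rule: "Events that are coded with multiple MedDRA Terms will be counted as separate event". It makes no exception for any category of event.

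Table 3.5.1 applies this rate to four summary rows: "Number of Adverse Events, Serious Adverse Events, Fatal Adverse Events and Number of Adverse Events Causing Treatment Discontinuation". The title is the same in the RA, PsA, AS and All Patients sets. Tables 3.5.2 and 3.5.3, by system organ class and preferred term, also count events.

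Patients are counted in tables 3.1, 3.2, 3.3 and 3.7.1 and, for All Patients, in 3.8.1. None of these is expressed per unit of exposure. In the per-year tables the numerator is "Number of patients treated in that year with at least one adverse event in that year", over the patients treated in that year. In the cumulative tables the denominator is all patients.

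Protocol section 3 states that if treatment "is permanently discontinued for any reason, patients will be discontinued from the study". It also asks for adverse events up to 3 months after the last administration.

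**The concern.** A patient dies once. In a row of fatal events per patient-year, a reader expects the numerator to be close to the number of deaths. Under the SAP's rules it is the number of fatal records or coded terms, so the row can exceed the death rate by an amount that the table does not show. The same applies to a permanent stop, which ends participation and can occur only once per patient.

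The second gap concerns the measure itself. Follow-up varies: SAP section 1.5 has treatment duration categories from 0 to 3 months up to more than 60 months. The exposure-based table is therefore where a reader will look for a rate that allows for follow-up. What it offers combines how many patients are affected with how often the same patient is affected. A patient-level rate that allows for exposure is not planned anywhere.

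**Working it through.** The documents state no adverse event rate, so there is no figure to reproduce. As an input check, 2836 + 1127 + 1957 = 5920, which agrees with SAP section 1.2. Every event count, exposure and clustering value below is an assumption.

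**1. Can one death count twice?** Protocol section 3.3.6 records outcome and action taken for each event, so two records may both carry a fatal outcome or both lead to the same stop. The SAP's multiple-coding rule also splits one record into several events. No rule in either document reduces these to one per patient. On the text, a death coded to two terms adds 2 to the fatal numerator.

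**2. Size for the fatal row.** With D deaths, m fatal records or terms per death, and PY patient-years:
- patient-based rate = 100 × D / PY
- event-based rate = 100 × D × m / PY
- ratio = m, whatever D and PY are

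Assume 59 deaths (1% of 5920) and mean exposure of 3 years, so PY = 5920 × 3 = 17,760. The patient-based rate is 100 × 59 / 17,760 = 0.33 per 100 PY. The event-based rate is 0.42, 0.50 or 0.66 for m = 1.25, 1.5 or 2. With mean exposure from 2 to 5 years, the patient-based rate runs from 0.50 to 0.20, and the event-based rate at m = 2 from 1.00 to 0.40.

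**3. Event rate against first-event rate.** Assume 5 years of follow-up for everyone, event rate r per patient-year, and gamma-distributed frailty with variance θ. Then S(t) = (1 + θrt)^(−1/θ), and the first-event rate is (1 − S(5)) divided by the integral of S from 0 to 5. This reduces to 0.5r × (1 + 1/(1 + 2.5r)) at θ = 0.5, and to r/√(1 + 10r) at θ = 2.

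| Event rate per 100 PY | First-event rate, θ = 0.5 (gap) | First-event rate, θ = 2 (gap) |
|---|---|---|
| 1 | 0.99 (1.2%) | 0.95 (4.7%) |
| 2 | 1.95 (2.4%) | 1.83 (8.7%) |
| 5 | 4.72 (5.6%) | 4.08 (18.4%) |
| 50 | 36.1 (27.8%) | 20.4 (59.2%) |

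**4. A more concentrated pattern.** Take PsA with 1127 × 3 = 3381 PY and 100 affected patients, of whom 90 have one event and 10 have ten each. The event rate is 100 × 190 / 3381 = 5.62 per 100 PY. Affected patients over full exposure come to 100 × 100 / 3381 = 2.96, and the ten patients supply 100/190 = 53% of the events. This is extreme clustering. The ratio of variance to mean count is (1090 − 1127 × 0.1686²)/190 = 5.57, and 5.57 = 1 + 0.1686θ gives θ of about 27. It shows what the measure permits, not what to expect.

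**5. What the other tables provide.** Table 3.2.1 gives, for each year, the share of patients treated in that year who had any, serious, fatal or treatment-stopping events. Patients who left earlier are out of the denominator, but a patient treated for one month of the year weighs the same as one treated for twelve. Tables 3.1 and 3.3 make no allowance for length of follow-up.

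**The case against.** Events per patient-year is a legitimate measure of burden. The protocol promises only descriptive frequencies and percentages, and neither document makes comparing RA, PsA and AS an objective. The row is labelled as fatal events rather than deaths, and tables 3.1.1, 3.2.1 and 3.3.1 already count patients with fatal and treatment-stopping events, so a careful reader could detect duplication. All of this stands. It is the reason to keep the event rate and to ask for an addition rather than a replacement. It does not supply a patient-based rate per unit of exposure, and it does not stop the fatal row from exceeding the death rate.

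Four stronger readings are tempting, and the documents do not support them.
- *The study would have no yearly patient-level risk.* Table 3.2.1 gives one, with part-years as its weakness.
- *Discontinuation can occur only once per patient.* The SAP row does not say permanent, SAP section 1.5 notes temporary stops, and protocol section 4.1.1 speaks of both kinds. The argument is firm for death, and for discontinuation only where the stop was permanent.
- *Serious or fatal event rates are more than double the first-event rates.* The 59% gap belongs to an assumed 50 events per 100 PY with strong clustering. It does not carry over to rare events.
- *Table 3.4.1 also needs patient counts.* It has no exposure denominator, and 3.1.1 already gives those counts.

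**Conclusion.** The point holds in two parts. First, on the SAP's text, the fatal row of table 3.5.1 can count one death several times, and the discontinuation row can do the same for one permanent stop. The inflation factor for the fatal row is the mean number of fatal records or terms per death. This does not depend on exposure, but its value is unknown from the documents. Second, no table gives patients with a first event per patient-year. Under the frailty model with 5 years of follow-up and variance 0.5 to 2, this costs about 1 to 18% at assumed event rates of 1 to 5 per 100 PY. The loss is larger for common recurrent events, or if a few patients dominate more strongly than that range allows. The plan's event rate is not wrong as a measure of burden. It needs a patient-based rate beside it, and each death should count once.

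**What to change.** In table 3.5.1 for RA, PsA, AS and All Patients:

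1. Use patients, not events or coded terms, as the numerator of the fatal row. Do the same in the discontinuation row where the stop was permanent.
2. For the four summary rows (any, serious, fatal, treatment-stopping), add the number of patients with at least one such event, divided by exposure summed to the first such event, or to the end of exposure for patients without one.
3. State how events after the last dose enter this rate, since they are recorded for up to 3 months. State also the time origin, because SAP section 1.5 takes treatment duration for non-completers from a recorded total, if available, rather than from two dates.
4. Keep the event rate in its own column, labelled as events per patient-year.

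Table 3.4.1 needs no change. Extending the first-event rate to every system organ class and preferred term is optional. The cost is some SAP wording and slightly more output, from onset dates and exposure that the analysis already uses.

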3.1.1 Inclusion Criteria

- Patients with ongoing HUMIRA® (adalimumab) treatment who have been prescribed HUMIRA® (adalimumab) within local reimbursement guidelines.

- Patients must be willing to consent to data being collected and provided to Abbott Laboratories

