1. METHODOLOGY

The purpose of this statistical analysis plan is to provide detailed information on the statistical analysis of the data of the ProAct study. The plan is based on the quotation dated 18 October 2017 and the mail dated 4 April 2017.

1.1 *Study Objective*

To evaluate the effectiveness and safety of adalimumab for the treatment of rheumatoid arthritis (RA), psoriatic arthritis (PsA) and ankylosing spondylitis (AS) in real life clinical practice.

1.2 *Available data*

The questionnaires table, as received on 5 February 2018, contained 47378 records, of which 5947 baseline visits. This database has been adapted by hardcoding in the programmation in order to resolve inconsistencies, double patients, misclassification of visits, add additional visit CRF pages, add additional AE pages. A total of 5920 patients of which 2836 rheumatoid arthritis patients, 1127 psoriatic arthritis patients (of which 197 Oligoarticular PsA) and 1957 ankylosing spondylitis patients were included in the analysis.

The parameter DAS28 was entered in the database from the moment the new Belgium reimbursement criteria for Humira were in place (2010).

Visits were scheduled at baseline, months 3, 6, 9 and 12, then every 6 months till 5 years.

1.3 *Patient Population*

All patients are to be considered in the analysis.

1.4 *Data Handling*

All data handling rules used during the analysis will be described in the section Methodology of the Statistical Report.

‘LT’ visits are visits added in the database for patients who were lost to follow-up in order to close the patient in the database. These visits will not be taken into account for any analysis.

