1.5 Derived Data

- Study duration (year) = (visit date of last visit – visit date of baseline visit)/365.25

- Completed patients: patients with ≥ 1734 days study duration

- Treatment duration (year):

For completed patients:

(Date of last visit – Date of baseline visit)/365.25

For not completed patients:

Sum of number of weeks/52, months/12 and years patient has been on drug documented on the last visit

If missing: (Date of last visit – Date of baseline visit)/365.25

Note: Some patients stopped Humira temporally. The periods of not taken Humira are not taken into account for the analysis. These patients will be considered as having taken Humira during the complete study.

- Treatment duration category:

0 to 3 months

> 3 to 6 months

> 6 to 9 months

> 9 to 12 months

> 12 to 18 months

> 18 to 24 months

> 24 to 30 months

> 30 to 36 months

> 36 to 42 months

> 42 to 48 months

> 48 to 54 months

> 54 to 60 months

> 60 months

- For the purpose of the analysis of the evolution of parameters over time, follow-up visits will be classified into time windows, defined upon the number of days between Visit 1 and the date of each subsequent visit (PERIOD = Date of follow-up visit - Date of Visit 1)

- Period = Date of visit – Date of baseline visit

- Month 3 window: $1 \leq \text{period} \leq 137$ days

- Month 6 window: $138 \leq \text{period} \leq 228$ days

- Month 9 window: $229 \leq \text{period} \leq 319$ days

- Month 12 window: $320 \leq \text{period} \leq 456$ days

- Month 18 window: $457 \leq \text{period} \leq 639$ days

- Month 24 window: $640 \leq \text{period} \leq 821$ days

- Month 30 window: $822 \leq \text{period} \leq 1004$ days

- Month 36 window: 1005 <= period <= 1186 days
- Month 42 window: 1187 <= period <= 1368 days
- Month 48 window: 1369 <= period <= 1551 days
- Month 54 window: 1552 <= period <= 1733 days
- Month 60 window: 1734 <= period <= 1916 days

Each visit will be classified in a time window. If the date of the visit is completely missing, it will be assumed that the visit took place on the target day of the window as indicated on top of the follow-up page. If more than one follow-up visit is classified into the same time window, the visit closest to the target day is retained. If within a time window there are two visits at the same distance from the target day, the visit which comes first (e.g. before the target date) is retained. If there are two visits on the same date, the first record is retained.

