 - 1.7.4 Number of DMARDs Used
 - 1.7.5 Frequency of Use of Each Type of DMARD
 - 1.7.6 Combination of Types of DMARD Used
 - 1.8 Study Duration
 - 1.9 Results of the Tests

- 2 Follow-up Data**
 - 2.1 Treatment Duration
 - 2.1.1 Treatment Duration
 - 2.1.2 Treatment Duration Category
 - 2.1.3 Treatment Duration Broken Down by Year of Start Treatment
 - 2.1.4 Treatment Duration Broken Down by DAS28 Category at Window 2 (Month 6)
 - 2.2 Physician's Assessment of Disease Activity
 - 2.2.1 Physician's Assessment of Disease Activity in Each Window
 - 2.2.2 Physician's Assessment of Disease Activity - Difference from Baseline
 - 2.3 Clinical Examination
 - 2.3.1 Joint Assessment (tender joints count, swollen joints count) in Each Window
 - 2.3.2 Joint Assessment (tender joints count, swollen joints count) – Difference from Baseline
 - 2.3.3 Inflammatory Parameters (CRP, ESR) in Each Window
 - 2.3.4 Inflammatory Parameters (CRP, ESR) – Difference from Baseline
 - 2.3.5 Physical Function (HAQ %) in Each Window
 - 2.3.6 Physical Function (HAQ %) – Difference from Baseline
 - 2.3.7 Physical Function (HAQ %) - Number of Patients with >7.33% Reduction from Baseline
 - 2.3.8 DAS28 in Each Window
 - 2.3.9 DAS28 – Difference From Baseline
 - 2.3.10 DAS28 Category in Each Window

3 Adverse Events

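### Table 2.1.3 can show longer treatment duration for early start years when persistence is unchanged, because patients enrol already on drug and non-completers are timed by a different clock from completers

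*SAP*

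**What the plan says.** SAP section 2 lists "2.1.3 Treatment Duration Broken Down by Year of Start Treatment" for RA and repeats it for PsA and AS. Only the title is given. It does not say whether the year is that of the first adalimumab dose or of the baseline visit.

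SAP 1.5 defines treatment duration by two rules:

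- **Completers.** The group is defined as "Completed patients: patients with ≥ 1734 days study duration". Duration is last visit minus baseline visit, so time on drug before enrolment is left out.
- **Non-completers.** Duration is "Sum of number of weeks/52, months/12 and years patient has been on drug documented on the last visit". If that is missing, it is last visit minus baseline visit. The SAP does not say whether the documented time starts at first dose or at enrolment.

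Protocol 3.1.1 admits "Patients with ongoing HUMIRA® (adalimumab) treatment", and protocol section 3 says the prescription precedes enrolment. Neither limits the gap between starting the drug and the baseline visit. Protocol section 3 also ends follow-up when the drug is permanently stopped.

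On calendar time, SAP 1.2 says only "The questionnaires table, as received on 5 February 2018". Neither document gives a first or last enrolment date, a data cut-off, or a censoring or delayed-entry rule for treatment duration.

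**The concern.** A breakdown of duration by start year invites the reader to compare persistence across years. Three features of the plan can make those rows differ when persistence is the same.

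1. **Delayed entry.** A patient who started well before enrolment could enter only because the drug had not yet been stopped. If stopping is more frequent soon after start, such patients have longer durations after enrolment than patients enrolled at start.
2. **Mixed clocks.** If documented time on drug runs from first dose, a non-completer who enrolled late carries the pre-enrolment years into the table, and a completer does not. This lengthens rows with long gaps before enrolment, which are likely to be the early start years.
3. **No censoring.** Anyone under 1734 days is classed as not completed, whether the patient stopped, was lost, or was still on drug at the last recorded visit. The observed time is then summarised as if it were the full duration.

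Protocol section 2 names long-term use as an objective. A reader could take the table to show that persistence fell over calendar time when nothing had changed.

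**Working it through.** The documents state no expected treatment duration, so there is no plan figure to reproduce. The check asks what the table would show if persistence were identical for everyone.

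**Inputs from the documents.** Completer threshold 1734 days, which is 1734/365.25 = 4.75 years; planned follow-up 5 years; table received 5 February 2018.

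**Assumptions, not in the documents.** Time on drug is Weibull, S(t) = exp(−λt^k), with 50% on drug at 5 years, so λ = ln 2/5^k. One patient enrols at start and another 2 years after start. The last visit falls at stopping or at 5 years, and nobody is lost. Documented time on drug runs from first dose.

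**Step 1. One baseline clock for everyone (delayed entry alone).** The mean is ∫ S(t) dt over 0 to 5 for entry at start, and ∫ S(2+t)/S(2) dt over 0 to 5 for entry at 2 years.

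| Shape k | Entry at start (years) | Entry 2 years later (years) | Excess |
|---|---|---|---|
| 0.6 | 3.29 | 3.96 | 20% |
| 0.7 | 3.38 | 3.85 | 14% |
| 0.8 | 3.47 | 3.76 | 8% |
| 1.0 (constant) | 3.61 | 3.61 | 0% |

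**Step 2. The SAP's two clocks.** Each non-completer who entered at 2 years gains 2 years. The completer share is P = S(2+4.747)/S(2), and the mean becomes the step 1 mean plus 2(1−P).

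- k = 0.7: P = 0.6126, so 3.852 + 2 × 0.3874 = 4.63, against 3.38 (37% longer). Of the 1.24-year excess, 0.77 comes from the non-completer rule and 0.47 from delayed entry.
- k = 1.0: P = 0.5178, so 3.607 + 2 × 0.4822 = 4.57, against 3.61 (27% longer). All of this comes from the non-completer rule.

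**Step 3. Whole-table simulation.** Persistence is the same in every start year (assumed median 4 years), with starts from late 2003, an assumed study opening in 2007 and last enrolment at the end of 2012. Means in years:

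| Clock | Shape | 2003 starters | 2007 and later |
|---|---|---|---|
| SAP rule | 1.0 | 5.11 | 3.35 |
| SAP rule | 0.7 | 5.08 | 3.18 |
| All from baseline | 1.0 | 3.36 | 3.35 |
| All from baseline | 0.7 | 3.78 | 3.18 |
| All from start, delayed entry ignored | 1.0 | 6.49 | 3.35 |

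Under the SAP rule the table falls with no true change. A common clock alone does not repair it: from baseline it still falls at shape 0.7, and from treatment start without delayed entry it falls further.

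**Step 4. Late rows.** 5 February 2018 minus 1734 days is 8 May 2013, and minus 5 years is 5 February 2013. Only patients enrolled after those dates could be cut short. With an assumed constant stopping rate h = 0.15 per year, the mean is (1−exp(−hc))/h. Here c is the smaller of 5 years and the time to 5 February 2018, and the result is averaged over baseline dates in the year. That gives 3.52 years for baseline years to 2012, 3.32 for 2013, 2.78 for 2014 and 2.15 for 2015. If enrolment ended by early 2013 the effect is nil.

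**The case against.** - **The completers' clock works the other way.** A reader might infer that counting completers from enrolment creates the fall. It does not: it removes pre-enrolment time, mostly from early starters. In step 3 the 2003 starters average 6.49 years if all are counted from treatment start and 5.11 under the SAP rule. The objection stands against that reading, but not against delayed entry or the non-completer rule.
- **Year of start may mean baseline year.** The visit windows, adverse-event years and completers' duration in SAP 1.5 all run from baseline, and protocol 3.3.3, 3.3.4 and 3.3.7 name no adalimumab start date among the baseline items. On this reading the row mismatch vanishes for completers. The objection stands as a reason to define the term. It does not remove the mixed clocks, because a non-completer's documented time could still reach back before baseline.
- **Documented time may start at enrolment.** In that case the step 2 excess vanishes and only step 1 remains, which is zero at a constant stopping rate. A falling rate is an assumption.
- **February 2018 is a receipt date.** A reader might infer that late rows are certainly truncated. The documents give no cut-off and no enrolment dates, so this can be stated only as a condition.
- **The table is descriptive.** Protocol section 5 rules out inferential techniques, and the tests in SAP section 2 concern baseline data only. No error rate is affected. A descriptive table can still mislead.

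**Conclusion.** The point holds in a conditional form. As written, table 2.1.3 can show a fall in treatment duration across start years with no change in persistence. The sources are delayed entry, the separate non-completer clock and the absence of censoring.

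If year of start is the year of first dose and documented time runs from first dose, the illustrated excess for entry 2 years after start is 1.24 years (37%) at shape 0.7 and 0.96 years (4.57 − 3.61; 27%) at a constant rate. If everyone were timed from baseline, it would be 8% to 20% for shapes 0.8 to 0.6 and nil at a constant rate. These sizes rest on an assumed persistence curve and an assumed 2-year gap.

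The documents do not support saying that the completers' baseline clock causes the fall, or that late rows are necessarily truncated. The matter should be settled before the table is interpreted, but it concerns a misleading descriptive trend and not the validity of a test.

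**What to change.** In SAP 1.5 and for table 2.1.3 in each indication:

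1. Define year of start as the year of first adalimumab dose, and say where that date is recorded.
2. For this table, replace the two duration rules with time from treatment start for all patients. Let each patient enter the risk set at the baseline visit (left-truncated Kaplan-Meier).
3. Count permanent discontinuation as the event, and censor patients still on drug or lost at their last visit.
4. State the first and last enrolment dates and the data cut-off.

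If baseline year is preferred as the row, count all patients from baseline, split each row by time from treatment start to baseline, and censor in the same way. Changing the row without changing the clocks would leave the non-completer problem in place.

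The cost is SAP wording and one re-run table per indication. Early start years may have few patients at risk at short durations, so those parts of the curves will be imprecise. Patients with no recorded start date drop out of the start-year version, and their number should be reported.
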